3.7 TRIAL MANAGEMENT GROUP AND CLINICAL TRIALS UNIT RESPONSIBILITIES

The TMG will consist of the Protocol Committee members (Section 3.3) plus trial manager(s), data manager and other key trial staff as required.

The CTU will act on behalf of the Sponsor and will be responsible to the TMG to ensure that all of the Sponsor's responsibilities are carried out. The responsibilities include (but are not limited to):

- report to the TSC
- maintain the Trial Master File
- identify trial sites
- confirm all approvals are in place before release of the trial treatment and the start of the trial at a site
- provide training about the trial
- provide study materials
- data management centre
- Investigational Medicinal Product management
- 24-hour advice and unblinding service
- give collaborators and patients regular information about the progress of the study
- respond to any questions (e.g. from collaborators and patients) about the trial
- ensure data security and quality and observe data protection laws

- safety reporting
- ensure trial is conducted in accordance with the ICH GCP including trial monitoring
- statistical analysis
- publication of trial results

3.8 CONTACTING THE CTU IN AN EMERGENCY

For urgent enquiries, adverse event reporting and unblinding queries investigators and patients can contact the 24-hour telephone service provided by the CTU. This number is given in the Investigator's Study File and the Patient Alert Card.

3.9 PUBLICATION AND DISSEMINATION OF RESULTS

The trial protocol and results will be published in peer-reviewed journals. All publications will follow the CONSORT statement.²¹ Links to the publication will be provided in all applicable trial registers. Dissemination of results to patients will take place via the media, trial website (statinwise.lshtm.ac.uk) and relevant patient organisations. Collaborating investigators will play a vital role in disseminating the results to colleagues and patients.

The success of the trial depends entirely upon the collaboration of nurses and doctors in the participating practices and those who hold key responsibility for the trial. Hence, credit for the study will be assigned to the key collaborator(s) from a participating site as it is crucial that those taking credit for the work have actually carried it out. The results of the trial will be reported first to trial collaborators.

3.10 FINANCIAL SUPPORT

The StatinWISE trial is funded by the NIHR Health Technology Assessment programme. Funding for this trial covers trial materials, meetings and central organisational costs. The design and management of the study are entirely independent of the manufacturers of atorvastatin, which is not a new product.

4. ABBREVIATIONS USED

AE	Adverse Event
ALT	Alanine aminotransferase
AR	Adverse Reaction
CK	Creatinine Kinase
CONSORT	Consolidated Standards Of Reporting Trials
CRF	Case Report Form
CTU	Clinical Trials Unit
CVD	Cardiovascular Disease
DMC	Data Monitoring Committee
GP	General Practitioner
GCP	Good Clinical Practice
GMP	Good Manufacturing Practice
ICH GCP	International Conference on Harmonisation of Good Clinical Practice
IMP	Investigational Medicinal Product
IMPD	Investigational Medicinal Product Dossier
LSHTM	London School of Hygiene & Tropical Medicine
mg	milligram
MOP	Manual of Operating Procedures
NICE	National Institute for Health and Care Excellence
PI	Principal Investigator
PSF	Product Specification File
QP	Qualified Person
RCT	Randomised Controlled Trial
SAE	Serious Adverse Event
SAR	Serious Adverse Reaction
SmPC	Summary of Product Characteristics
SUSAR	Suspected Unexpected Serious Adverse Reaction
TMG	Trial Management Group
TSC	Trial Steering Committee
VAS	Visual Analogue Scale

Appendix 1 StatinWISE Trial assessment timelines

	Database search	PIS posted to eligible patients	Baseline Visit	TP1 (month 1-2)	TP2 (month 3-4)	TP3 (month 5-6)	TP4 (month 7-8)	TP5 (month 9-10)	TP6 (month 11-12)	Follow-up Visit (F2F/Phone)	Secondary outcome data capture
SCREENING											
Trial team performs GP practice patients' list screening to identify potentially eligible patients	x										
GP reviews screening list and confirms patients are clinically eligible		x									
Trial team posts PIS with reply slip		x									
Patients contact trial team to arrange Baseline visit		x									
ENROLMENT											
Patients attend enrolment visit with Research Nurse and sign consent form			x								
Research Nurse completes the Baseline Form on electronic trial database. Baseline data will include: - Personal Details - Demographic data - Eligibility assessment - General medical history which may include blood test to measure total non-fasting cholesterol if none available in notes - Randomisation data			x								

	Database search	PIS posted to eligible patients	Baseline Visit	TP1 (month 1-2)	TP2 (month 3-4)	TP3 (month 5-6)	TP4 (month 7-8)	TP5 (month 9-10)	TP6 (month 11-12)	Follow-up Visit (F2F/Phone)	Secondary outcome data capture
ENROLMENT											
Patients are randomised and trained on data entry tool of their choice			x								
TREATMENT PERIOD											
IMP posted to patients' address				x	x	x	x	x	x		
Patients confirm receipt of IMP				x	x	x	x	x	x	x	
Patients take study medication orally once daily				x	x	x	x	x	x	x	
Reminder to submit outcome data				x	x	x	x	x	x	x	
Patients enter outcome data and report any adverse events				x	x	x	x	x	x	x	
Patients post unused IMP to Pharmacy				x	x	x	x	x	x	x	
IMP accountability by Pharmacy				x	x	x	x	x	x	x	
Trial newsletter sent to patients						x			x		x
FOLLOW-UP											
Individual results ready to disclose										x	
Appointment (face-to-face or telephone call) with Research Nurse to discuss individual results										x	
END OF TRIAL											
Research Nurse telephones patients to record outcome data											x

Appendix 2: StatinWISE Baseline data form

1. Patient Initials				2. Patient Screening ID				-				3. Site ID			
4. Visit date	dd/mm/yyyy			5. Gender											
6. Ethnicity	a. White: (i) British (ii) Irish (iii) Traveller (iv) Other b. Black: (i) African (ii) Caribbean (iii) Black British (iv) Other c. Asian: (i) Asian British (ii) Indian (iii) Pakistani (iv) Chinese (v) Other d. Mixed e. Other: (describe) _____												Circle main group and sub-group		
7. Age	 		Years												

Patient Personal Details: The following information is needed for trial management purposes (sending trial medication and reminders) only and will not be collected as part of the trial database.

A. Full name	First name		Last name			
B. Postal address	House number/Name					
	Street name					
	Town/City					
	Postcode					
C. Email (primary)			D. Email (secondary)			
E. Home Telephone			F. Mobile number			

ELIGIBILITY ASSESSMENT (Circling any RED box means patient is NOT eligible)			Eligibility Please circle	
8. Written informed consent obtained?			YES	NO*
9. Is the patient aged 16 and over?			YES	NO*
10. Patient has a clinical reason for treatment with atorvastatin 20mg daily?			YES	NO*
11. Used statin within the last 3 years?			YES	NO*
12. Is patient considering discontinuation of their statin due to muscle related adverse effects OR Has patient stopped taking a statin due to muscle related adverse effects?			YES	NO*
13. Can atorvastatin 20mg daily be started or continued in the GP's opinion?			YES	NO*
14. Has patient had previously documented ALT levels at or above three times the upper limit of normal (ULN)? Test date: dd/mm/yyyy (must be within 3 months of visit) Result:    iU/L			YES*	NO
15. Does the patient have persistent, generalised, unexplained muscle pain (whether associated or not with statin use) and have creatinine kinase (CK) levels greater than 5 times the upper limit of normal? Test date: dd/mm/yyyy (must be within 3 months of visit) Result:    U/L			YES*	NO

*if circled, patient is NOT eligible

PATIENT GENERAL MEDICAL HISTORY

16. Symptoms experienced during statin use that the patient believed were caused by the statin:

(a) Muscle pain	YES/NO	(f) Sore throat	YES/NO
(b) Joint pain	YES/NO	(g) Digestive problems	YES/NO
(c) Muscle weakness	YES/NO	(h) Headache	YES/NO
(d) Tiredness/fatigue	YES/NO	(i) Feeling sick	YES/NO
(e) Nosebleeds	YES/NO		

17. Does the patient think something other than statin may have caused their muscle pain? YES/NO

17(a) If YES to Question 17, please describe:

18. Does the patient have any history of cardiovascular disease? YES/NO

18a. If YES to Question 18, please indicate all that apply :

(a) Angina or diagnosed coronary heart disease	YES/NO	(c) Previous ischaemic stroke	YES/NO
(b) Previous myocardial infarction	YES/NO	(d) Peripheral vascular disease	YES/NO
(e) Other	YES/NO	(If yes, describe)	_____

19. Current use of high blood pressure medication? YES/NO

20. Blood pressure measurement (mmHg):

					
----------------------	----------------------	----------------------	----------------------	----------------------	----------------------

a. Systolic b. Diastolic

21. Diabetes? YES /NO

22. Smoking status: (a) non-smoker (b) ex-smoker (c) current smoker

23. Total cholesterol measurement [mmol/L] (within last 3 years):

	
----------------------	----------------------

If no reading, in line with NICE guidelines, organise non-fasting blood test for total cholesterol

24.

a. Height: cm

b. Weight: Kg

25. QRISK2 score:

26. Record all current medication:

Name of drug (generic)

Total daily dose and unit

1.

27. Consent to participate in genetic study? YES/NO

27a. Blood sample taken? YES/NO

27b. Blood shipment reference:

RANDOMISATION DATA

28. Is patient fully eligible? YES/NO

29a. Date of Randomisation?

					
DD	MM	YYYY			

29b. Time of Randomisation? (24 hour clock)

			
HOUR		MINS	

30. Randomisation Number:

			
----------------------	----------------------	----------------------	----------------------

31. Method of data collection chosen?

(a) Online system	(b) Mobile application
(c) Phone call	(d) Paper CRFs

31a. App successfully installed?

YES/NO

32. Training provided on method chosen?

YES/NO

33. Form completed by:

34. Date:

This data should be collected directly onto the online trial database (detail in your study file). If you are unable to enter this data, call [name]

Appendix 3: StatinWISE End of Trial data form

End of Trial Form (Month 15) / Early Withdrawal

1. Did the patient complete 6 Treatment Periods?

YES

A.1. Has the Research Nurse/GP spoken to the patient to discuss their individual results?

(i) YES

(ia) Date seen: _____ dd/mm/yyyy

(ii) NO – (please arrange an appointment).

(iia) Date of appointment: _____ dd/mm/yyyy

A.2. Has the patient seen his/her GP since end of Treatment Period 6?

(i) YES

(ii) NO (please remind the patient to book an appointment)

(iia) Date reminder done: _____ dd/mm/yyyy

A.3. Has the patient been given a statin prescription in the 4 weeks since Treatment Period 6 ended?

(i) YES

(ia) Name of Statin: _____

(ib) Dose of statin: _____

(ii) NO

A.4. Has the patient found their own trial results helpful to reach the decision as to whether to continue statin use?

YES/NO

NO

B.1. Please tick reason why the patient did not complete 6 treatment periods:

Lost to follow-up

Early withdrawal

Death

B.2. Lost to follow-up:

Date of last contact with patient? _____

Dd/mm/yyyy

B.3. If Early withdrawal, give reason:

- a. withdrawal of informed consent
- b. intolerable muscle symptoms*
- c. clinical concern*
- d. other*

*: please enter details here: _____

B.4. Has the patient contacted their GP to discuss reason for withdrawal?

(i) YES

(ia) Date seen: _____ dd/mm/yyyy

(ii) NO – (advise patient to contact GP).

B.5. Has the Research Nurse/GP spoken to the patient to discuss their individual results?

(i) YES

(ia) Date seen: _____ dd/mm/yyyy

(ii) NO – (please arrange an appointment).

(iia) Date of appointment: _____ dd/mm/yyyy

B.6. Death (SAE report form must be completed)

B.6.a. Date of death: _____ dd/mm/yyyy

B.6.b Cause of death (either autopsy report or clinical judgement if autopsy not available):

B.6.c. Date SAE form completed: _____ dd/mm/yyyy

C.1. This form was completed by: _____ Date: dd/mm/yyyy

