2.4 SAMPLE SIZE

A sample size of 64 participants provides approximately 90% power to detect a treatment effect of at least 10mm, assuming a Type I error of 5%. Allowing for loss to follow-up of 40% of participants through the trial inflates the required sample size to 107 participants.

Period effects (changes in underlying VAS pain score due to factors other than randomised treatment, e.g. seasonal, activity-related, etc.), variability in individual statin effects across patients, and imperfect adherence to the assigned treatment were investigated by further detailed simulations. VAS pain scores are not normally distributed, since they are bounded (0-100mm) and can display large fluctuations in response. Therefore, further power calculations were performed drawing the outcome from a Beta distribution, and from a distribution with normal variance components on a logit scale, to assess the robustness of the sample size estimates to the distribution chosen. These factors all have the effect of decreasing power, thus increasing the sample size required. An approximate 80% increase in the sample size required in the absence of these effects provided approximately 90% or more power across a plausible range of these potential effects, thus we determined that a final sample size of 200 was required.

Multiple testing: Rather than making formal adjustments for multiple testing, we follow an approach advocated by Pocock²⁵ of clearly specifying our primary analysis (which provides a single test for treatment effect), while explicitly presenting and interpreting all other tests as secondary analyses.

Power for individual N-of-1 trials: In order to increase the statistical power for the analysis of individual N-of-1 trials, we will ask participants to report symptoms daily in the last week of each period, rather than once per period. Full adherence through the trial will provide between 55 and 70% power to detect effects of 10mm or greater for individual treatment comparisons.

Estimates of recruitment and retention rates: We anticipate that some patients will not complete data in each treatment period, and that some will not complete their 12-month follow-up. By designing this study as a series of N-of-1 trials, which offer individual participant benefit in the form of an individualised estimate of effect, we hope to minimise this type of dropout. However, we have accounted for this in our sample size calculation by allowing for 40% loss to follow-up.

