2.10.5 EARLY WITHDRAWAL OF PATIENTS FROM THE TRIAL

A patient is free to change their minds about participation at any time. We would advise that the patient see their GP to discuss future routine care. A GP can withdraw a patient at any time if clinical

concerns arise or if the patient presents with any reason to stop atorvastatin as described in the Summary of Product Characteristics for Atorvastatin 20 mg (Appendix 8). In each case, an end of trial form (Appendix 3) should be completed.

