2.13 OUTCOME MEASURES

Primary outcome: The primary outcome is self-reported 'muscle symptoms', defined as pain, weakness, tenderness, stiffness or cramp to the body of any intensity, recorded where the participant believes they are associated with the study medication; these are the symptoms most commonly reported by patients and are often the reasons for discontinuation. The primary outcome will be assessed by the mean difference in VAS scores (range 0 to 100) between treatment periods with the trial treatment and treatment periods with placebo, estimated via a linear mixed model.

Secondary outcomes: Secondary outcomes relating to participant belief about the cause of their muscle symptoms, the site of muscle symptoms, how the muscle symptoms affected the participant and information about any other symptoms will be collected on the last day of each two-month treatment period, using a questionnaire (Appendix 5). The other secondary outcomes are adherence

to medication, the participant's decision about statin treatment following the trial, and whether they found their own trial result helpful.

Specifically, secondary outcomes will be:

1. The proportion of patients with muscle symptoms during each two-month period who report that they believe their symptoms were caused by the study medication, comparing periods of IMP treatment with placebo.
2. Site of muscle symptoms (single or multiple; head and neck/upper limbs/lower limbs/trunk).
3. Among patients reporting muscle symptoms, the difference in mean VAS scores (range 0 to 100) for the following, comparing periods of IMP treatment with placebo:
 - a. General activity
 - b. Mood
 - c. Walking ability
 - d. Normal work (includes both work outside the home and housework)
 - e. Relations with other people
 - f. Sleep
 - g. Enjoyment of life
4. Other symptoms that the patient believes can be attributed to the study medication (grouped: musculoskeletal; gastrointestinal; respiratory; neurological; psychological; other).
5. Adherence to study medication as assessed by: (a) self-report and (b) counting pills remaining in returned packages, and the relationship between adherence and muscle symptoms.
6. Participant decision regarding future statin use and the relationship to their primary outcome.
7. Whether patients found their own trial result helpful in making the decision about future statin use.

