1.8 DEFINITION OF SECONDARY OUTCOMES

The following secondary outcomes will be collected once at the end of each of the 6 treatment periods, via the patient questionnaire form (Appendix 2).

- Whether or not the patient experienced muscle symptoms that they believe were caused by the study medication (yes/no/don't know).
- Site of muscle symptoms:
 - Single/multiple
 - head and neck/upper limbs/lower limbs/trunk
- Visual Analogue Scale scores (range 0-10) for how the participant's muscle symptoms impact on the following:
 - General activity
 - Mood
 - Walking ability
 - Normal work (includes both work outside the home and housework)
 - Relations with other people
 - Sleep
 - Enjoyment of life

These are collected only if the participant reports muscle symptoms during that period. For comparisons between randomized treatments these VAS scores will be set to zero for participants who report no muscle symptoms in that period.

- Other symptoms that the patient believes can be attributed to the study medication. These will be entered as free text and grouped into: musculoskeletal/gastrointestinal/respiratory/neurological/psychological/other (not mutually exclusive categories).
- Adherence to study medication:
 - not at all/some days/most days/every day

Adherence will also be assessed in the following ways:

- number of pills remaining in returned packages (0-56; collected each treatment period)
- self-report ("took pill yesterday" - yes/no; collected daily during the last 7 days of each of the 6 treatment periods)

The final secondary outcomes will be collected in the end of trial interview with the participant:

- Participant decision regarding future statin use and the relationship to their primary outcome (patient has been given a statin prescription in 4 weeks following trial - yes/no).
- Whether patients found their own trial result helpful in making the decision about future statin use (yes/no).

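### The End of Trial form records the statin decision and the helpfulness of the result only for patients who completed six periods, although the protocol and SAP text set no such limit

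*Protocol*

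**What the plan says.** Protocol Appendix 3 is one form serving both month 15 and early withdrawal. It opens with "1. Did the patient complete 6 Treatment Periods" and splits on the answer.

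- **YES branch.** Item A.3 asks "Has the patient been given a statin prescription in the 4 weeks since Treatment Period 6 ended". The next item is "A.4. Has the patient found their own trial results helpful to reach the decision as to whether to continue statin use".
- **NO branch.** It starts at "B.1. Please tick reason why the patient did not complete 6 treatment periods". It then takes the date of last contact, the reason for withdrawal (intolerable muscle symptoms is option B.3b), whether the GP was contacted (B.4), whether individual results were discussed (B.5), and details of any death (B.6). It has no item on statin use or helpfulness.

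On early withdrawal, Protocol 2.10.5 says "In each case, an end of trial form (Appendix 3) should be completed". Protocol 2.10 confines the trial database to the content of the listed forms.

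Items A.3 and A.4 serve secondary outcomes 6 and 7 in Protocol 2.13. Outcome 6 is "Participant decision regarding future statin use and the relationship to their primary outcome"; outcome 7 is whether the result helped with that decision. Protocol 2.10.3 and SAP 1.2 have trial staff contact the patient about both at month 15. SAP 1.8 says "The final secondary outcomes will be collected in the end of trial interview with the participant". None of these places limits the contact or the outcomes to completers. SAP 2.3.2 relates both outcomes to the individual estimated effect and names no analysis population.

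On dropout, Protocol 2.4 says "we have accounted for this in our sample size calculation by allowing for 40% loss to follow-up".

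**The concern.** The text promises outcomes 6 and 7 for participants in general, but the form has somewhere to put them only for completers. Because the database holds form items only, the form decides what is kept. A patient who withdraws early can have individual results explained under B.5, yet what the patient then did about statins has no field.

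This matters because the link between individual result and later statin use is the only secondary outcome in the protocol synopsis, and the Introduction gives it as the reason for three further months of follow-up. Completing six periods may well be related both to the individual effect and to later statin use, since intolerable muscle symptoms is a listed reason for withdrawal. An association estimated in completers alone is therefore open to selection. Because the SAP names no population for these outcomes, a completers-only result could be reported as if it described everyone.

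**Working it through.** **1. Fields against outcomes.**

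| Outcome (Protocol 2.13) | Completed six periods | Did not complete |
|---|---|---|
| Individual results discussed | A.1 | B.5 |
| 6. Decision on statin use | A.3 | none |
| 7. Result found helpful | A.4 | none |

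A.3 is also dated from the end of Period 6, so it could not be put to someone who stopped earlier even if it stood in the other branch.

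**2. Can a non-completer have an individual effect?** Yes. All eight sequences in Protocol 2.8 start with one statin and one placebo period. Anyone who entered symptom scores in Periods 1 and 2 therefore has data on both treatments. Protocol 2.17 and SAP 1.10 require one score on each for the primary analysis. A patient withdrawing in Periods 3 to 6 can be in the primary analysis, have an individual effect, and have no value for outcomes 6 and 7. Some Period 2 stoppers qualify too, because Protocol 2.10.4 asks patients who stop treatment to go on reporting for the current period. A patient with data on one treatment only has no contrast to relate to a decision.

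**3. Does the SAP deal with the gap elsewhere?** The population rule in SAP 1.10 covers the symptom scores and the patient questionnaire, not the end-of-trial interview. The missing-data plan in SAP 2.3.4 is built around the mixed model. Neither covers outcomes 6 and 7.

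**4. The plan's dropout figure.** Inputs from Protocol 2.4: base size 64, loss 40%, a further increase of about 80%, final size 200.

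- 64 / (1 − 0.40) = 106.7, rounded up to 107. This reproduces the plan's figure.
- 107 × 1.8 = 192.6, consistent with 200.
- 0.40 × 200 = 80, leaving 120.

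So 80 is the most that the plan's own allowance would place in the NO branch. Protocol 2.4 says the allowance covers incomplete data within periods as well as failure to finish 12 months. A patient with gaps in the data may still complete six periods and answer A.3 and A.4.

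**5. Range for the number affected** (assumed non-completion rates; every completer assumed to answer).

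| Non-completion | No field for outcomes 6 and 7 | Answers available |
|---|---|---|
| 10% | 20 | 180 |
| 20% | 40 | 160 |
| 30% | 60 | 140 |
| 40% | 80 | 120 |

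**6. What the missing items could recover.** The documents do not say how many non-completers could be reached. Taking the ceiling of 80 and assuming that 25%, 50% or 75% are contactable gives 20, 40 or 60 more answers, for totals of 140, 160 or 180.

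**7. Timing.** Protocol 2.16 places the last contact 15 months after the first treatment day. A completer is then about 15 − 12 = 3 months past treatment. A patient who stopped in Period 2 (months 2 to 4 after starting) is 15 − 4 = 11 to 15 − 2 = 13 months past it.

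**The case against.** The strongest reply is that the plan does intend to ask. Protocol 2.10.3 and SAP 1.2 describe a month-15 contact with the patient, with no restriction to completers, and SAP 1.8 defines the outcomes just as generally. On that reading this is a mismatch between form and text, not a design that excludes early stoppers. That stands, and it rules out calling the secondary objective unanswerable. It does not close the gap, because an answer obtained at month 15 from a non-completer has no field on the form.

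A reader might go further and infer that 40% of patients are expected to stop early and be lost. The documents do not support this. The 40% is a sample-size allowance that mixes incomplete period data with loss to follow-up. Patients who have died, lost contact or withdrawn consent may be out of reach whatever the form says.

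A reader might also infer that the form keeps only those who tolerated 12 months of capsules, and so overstates continuation. That does not follow either. Under Protocol 2.10.4, some patients with intolerable symptoms may stay in on modified or interrupted treatment and can plausibly reach the end of Period 6. Intolerable symptoms do not show a large statin effect: the Introduction reports 7% dropping out for myalgia during a blinded placebo phase of another trial. Any comparison of restart rates would rest on assumed inputs, and would concern the overall rate, not the relationship that outcome 6 is about.

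Finally, copying A.3 unchanged into the NO branch would not work, and times since stopping would differ widely. Both points stand and shape the fix.

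**Conclusion.** The point holds as a gap in data collection. Following the documents, outcomes 6 and 7 are recorded for completers only. Contactable early withdrawals are lost, including those who have data on both treatments and are in the primary analysis. The relationship between result and decision is then estimated in a selected group.

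The number affected is at most 80 of 200 on the plan's allowance, and smaller to the extent that the allowance reflects incomplete period data. The number recoverable depends on how many can be contacted, which the documents do not give. The direction and size of any bias are unknown. That early stoppers are the patients the objective most concerns is a judgement the documents do not make.

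The conclusion rests on two readings: that the form is used as printed, and that the restriction of the database to form items is applied. The primary analysis is untouched. These are secondary outcomes for which the SAP specifies no test, but the change is cheap, and the answers are hard to obtain afterwards.

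**What to change.** 1. **Form.** Add a statin-use item and a helpfulness item to the NO branch of Appendix 3. Do not reuse the wording of A.3. Use an anchor that suits everyone, for example current statin use at the month-15 contact, asked in the same way in both branches, with the date of last trial treatment recorded. Ask helpfulness wherever results were discussed (A.1 or B.5).
2. **Protocol 2.10.3 and SAP 1.2.** State that the month-15 contact covers every randomised participant who still permits contact, whether or not six periods were completed.
3. **SAP 1.8 and 2.3.2.** Bring the definition of the decision outcome into line with the new item; A.3 can stay as an additional item for completers. Report decisions for all those contacted, with the number not reached. Relate decisions to the individual effect among those with data on both treatments. Show completers and non-completers separately, because time since stopping differs.

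The cost is two form items and one extra email or call per early stopper, with no added visit. Some will not respond, so the selection is reduced but not removed.
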